#### Serious Adverse Event (SAE)

A serious adverse event is defined as an event that: a) led to death, b) led to serious deterioration in health that either:

- 1) Resulted in life threatening illness or injury, or
- 2) Resulted in a permanent impairment of a body structure or body function, or
- 3) Required in-patient hospitalization or prolongation of existing hospitalization, or
- 4) Resulted in medical or surgical intervention to prevent life threatening illness or injury or permanent impairment to a body structure or a body function.

A planned hospitalization for pre-existing condition without a serious deterioration in health, is not considered to be a serious event.

### 10.2 Assessing and Recording Adverse Events

Each AE recorded must be documented on the Case Report Form. All serious and device related events must be reported immediately to Aziyo via telephone or email within 24 hours of the Investigator becoming aware of the event. The case report form will be submitted to Aziyo. The site will be contacted by Aziyo for additional information including, but not limited to:

- Description of the event and underlying cause (diagnosis), coexisting disease, or other. The AE should be recorded in standard medical terminology rather than the subject's own words when possible.
- Date of onset and date of resolution. If the event is present at the single postoperative visit it will be noted as unresolved.
- Intensity of the event: mild, moderate, or severe.
- Frequency of the event: single episode, intermittent, or continuous.
- Action taken: none, medication, procedure, medication and procedure, or other.
- Relationship to the device/procedure/surgery: not-related, possibly-related, or probably-related.

The Investigator must ensure that the details of the event are documented in the medical notes including full details of the outcome, in addition to recording the event on the case report form.

All procedure and device related serious adverse events that are associated with the use of the device will be evaluated in accordance with the protocol and the Sponsor's Incident/Event Reporting SOP. Any serious adverse event that requires a Medical

Device Report will be reported by the Sponsor to the FDA in accordance with Sponsor's Medical Device Reporting SOP. The site should contact:

[name] Aziyo Biologics, Inc. [name] [contact] Direct Office [contact] Fax [contact]

### 10.3 Possible Adverse Events

This study will capture events reported following the procedure and at follow up visits as reported by the PI and/or subject and from a review of medical records. The following device-related events have been identified as possible risks from the procedure:

- Allergic reaction to ECM
- Bleeding
- Calcification
- Fever
- Fibrosis
- Hematoma
- Infection
- Inflammation
- Seroma
- Undesired remodeling

There are no identified risks involved in participating in this post-market study.

### 11. Data Analysis

The primary endpoints are as follows:

- 1. The proportion of subjects with CanGaroo ECM related adverse events.
- 2. The incidence of major pocket infection.

Point estimates and exact 95% binomial confidence intervals will be provided for the true (population) values of these two endpoints.

The number and percentage of subjects with AEs and with device-related AEs will be presented by type of AE.

If possible, the rate of major pocket infection will be compared to the rate without use of the CanGaroo ECM device based on data from the U.S. Healthcare Cost and Utilization Project family of databases and/or contemporary literature.

Similarly, if possible, the rate of other AEs will be compared by type to the rate without use of the CanGaroo ECM device based on data from the U.S. Healthcare Cost and Utilization Project family of databases and/or contemporary literature.

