# **Study Synopsis**

OBJECTIVE	The objective of the SECURE Study is to actively gather additional information on the use of the CanGaroo ECM ® Envelope in a post market observational study.	
STUDY POPULATION	1000 subjects who have received CanGaroo ECM ® Envelope for an implantable electronic device placement.	
INDICATIONS FOR USE	CanGaroo ECM ® Envelope is intended to securely hold an implantable electronic device to create a stable environment when implanted in the body. The devices that may be used with the CanGaroo ECM ® Envelope include pacemaker pulse generators, defibrillators, or other cardiac implantable electronic device.	
ENDPOINTS	
 
The endpoints will be defined as:
 
1. The proportion of subjects with CanGaroo ECM related adverse events.
 
2. The incidence of major pocket infection.
 
	
EXAMINATION SCHEDULE	In-office wound check, 4-6 week, 3 month and an additional visit occurring at any time point after 3 month visit following an implantable electronic device procedure utilizing CanGaroo ECM ® .	
CLINICAL Parameters	
 
The following clinical data will be collected at post-operative visits:
 
Informed Consent
 
Demographic information
 
Risk factors for infection
 
Implant procedure
 
Type of device implanted
 
Information on CanGaroo ECM
 
CanGaroo ECM related adverse events
 
Information on infections
 
	
ANALYSIS	Outcomes for the SECURE Study will be compared to data collected from the U.S. Healthcare Cost and Utilization Project family of databases and/or contemporary literature.	

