### Endpoints

The endpoints will be defined as:

- 1. The proportion of subjects with CanGaroo ECM related adverse events.
- 2. The incidence of major pocket infection.

Major infection will be defined as 1) superficial cellulitis in the region of the CIED pocket with wound dehiscence, erosion or purulent drainage, 2) deep incisional or organ/space (pocket) surgical site infection, 3) persistent bacteremia or 4) endocarditis. Minor CIED infections include any that do not meet the definition of a major CIED infection. Documentation will also be provided in the medical records.

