# 6. Study Design

This is a multi-center post-market observational study. It is anticipated that up to 1000 subjects will be enrolled at up to 50 centers. Eligible candidates will be approached to ascertain interest in study participation at their initial follow up visit. If a subject is interested in participating and has had CanGaroo ECM used in their procedure, they will be asked to allow their physician to use their medical information from the procedure and four follow up visits. An informed consent will be provided to the patient and the patient will be asked to sign unless a Waiver of Documentation of Consent has been obtained. If a Waiver of Documentation of Consent is in effect, all elements of the approved informed consent will be provided verbally and the process will be documented in the subject study binder by the research staff for either method of consent.

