# 7. Study Population

The study population will consist of any subject who has received the CanGaroo ECM® Envelope for an implantable electronic device placement. Subjects will be considered enrolled into the study once they have provided informed consent and completed the procedure using the CanGaroo ECM Envelope. Before any subject can be enrolled, the site must have IRB approval from a centralized IRB or their specific institution IRB for the protocol and Informed Consent Form to be used at that site and Waiver of Documentation of Consent, if applicable.

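### Both primary endpoints are exact binomial proportions with no time horizon and no rule for incomplete follow-up, so the rates average over unequal follow-up and match no external rate's window

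*Combined protocol and SAP*

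**What the plan says.** The Endpoints text under Section 5 lists the proportion of subjects with device-related adverse events and "The incidence of major pocket infection". Major infection is defined there by four clinical criteria, with no time element. Section 11 makes both endpoints primary and gives one method: "Point estimates and exact 95% binomial confidence intervals will be provided for the true (population) values of these two endpoints".

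The Synopsis schedule has a wound check, a 4-6 week visit, a 3-month visit and "an additional visit occurring at any time point after 3 month visit". Section 9 ties that last visit to the investigator's standard of care and sets no upper limit. When a subject cannot attend, the site may collect data by telephone.

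Section 6 draws data from the whole course, since subjects allow the physician to "use their medical information from the procedure and four follow up visits". It also says: "Eligible candidates will be approached to ascertain interest in study participation at their initial follow up visit". Section 7 adds: "Subjects will be considered enrolled into the study once they have provided informed consent and completed the procedure".

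On external comparison, Section 11 says that, if possible, "the rate of major pocket infection will be compared to the rate without use of the CanGaroo ECM device", and it plans the same for other adverse events. The Synopsis attaches no condition: "Outcomes for the SECURE Study will be compared to data collected from" national database sources and/or literature.

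**The concern.** A cumulative proportion has a clear meaning only with a period attached. Here the period for each subject ends whenever that subject was last seen, which depends on site practice and on loss to follow-up. Two sites with the same infection risk could contribute different proportions because one sees patients at 4 months and the other at 12. The exact interval describes sampling error around that mixture and does not reflect how the mixture arose.

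What is at stake is interpretation. If the study rate differs from a database or literature rate, a reader could not tell whether the gap reflects the device, the length of follow-up, or which patients reached the first visit and consented.

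**Working it through.** **1. Is there a plan figure to reproduce?** No. The documents give up to 1000 subjects at up to 50 centers. They give no expected rate, loss rate, event timing or comparator rate. Every numerical input below other than n = 1000 is therefore an assumption, chosen to show how the estimate behaves.

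**2. Does other text fill the gap?** Telephone contact (Section 9), medical-record review (Section 10.3) and missing-data queries (Section 12.1) all reduce missed events. None sets a horizon, a denominator or a censoring rule. Section 10.2 requests onset dates, so a windowed count is feasible, but Section 11 does not call for one.

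**3. Unequal follow-up.** Assume an infection risk R = 2.0% by an assumed end of follow-up at 12 months, with a share s = 40, 60 or 80% of it by 3 months. The 3-month risk is r3 = R × s = 0.8, 1.2 or 1.6%. Assume 5, 10 or 20% are lost evenly before 3 months (l), and 30, 50 or 50% respectively have no contact after 3 months (o). The rest are f = 1 − l − o = 65, 40 or 30%. All enrolled form the denominator.

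- Rest last seen evenly over 3-12 months: crude rate = l·r3/2 + o·r3 + f·(r3 + (R − r3)/2).
- Rest all seen to 12 months: crude rate = l·r3/2 + o·r3 + f·R.

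Example with s = 40%, l = 5%, o = 30%: the first formula gives 0.02 + 0.24 + 0.65 × 1.4 = 1.17%, which is 1.46 times r3. The second gives 0.02 + 0.24 + 0.65 × 2.0 = 1.56%, which is 1.95 times r3.

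| Follow-up of the rest | Crude rate, nine scenarios | Ratio to 3-month risk |
|---|---|---|
| Evenly over 3-12 months | 0.90-1.69% | 0.94-1.46 (above in 6, equal in 2, below in 1) |
| All to 12 months | 1.08-1.82% | 0.98-1.95 |

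The ratio falls on either side of 1, so the assumptions decide the direction.

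**4. Choice of denominator.** With an assumed 10 events, the exact 95% results are 1.00% (0.48-1.83) for n = 1000, 1.11% (0.53-2.03) for n = 900 and 1.25% (0.60-2.29) for n = 800. Section 11 does not say which denominator applies.

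**5. Loss related to infection.** Assume a 3-month risk r = 1.2%, a proportion L lost evenly over 0-3 months, and lost subjects at k times the others' risk q = r/((1 − L) + L·k). Events seen are E = L·k·q/2 + (1 − L)·q. The all-enrolled ratio is E/r. The event-or-completed ratio is E/(1 − L + L·k·q/2)/r. Kaplan-Meier comes from integrating the observed hazard. Ratios to the true risk at L = 10%:

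| k | All enrolled | Event or completed | Kaplan-Meier |
|---|---|---|---|
| 1 | 0.950 | 1.055 | 1.000 |
| 2 | 0.909 | 1.009 | 0.956 |
| 3 | 0.875 | 0.971 | 0.919 |

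For L = 5-20% at k = 3 the ranges are 0.786-0.932, 0.971-0.980 and 0.867-0.955. Kaplan-Meier is exact when loss is unrelated to infection. At k = 3 all three read low, and the two binomials do not bracket the truth.

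**6. Who is enrolled.** If a share f of infections (here a new symbol) occurs before consent and a share m of those patients never enrols, the rate from implant is about 1 − f·m of the true risk. For f = 10-30% and m = 50-100%, that runs from 1 − 0.10 × 0.50 = 0.95 down to 1 − 0.30 × 1 = 0.70. No estimator in Section 11 can recover patients who are not in the data.

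**The case against.** The strongest reply is that this is a descriptive post-market study. Its objective is to gather information, it has no hypothesis, margin or success criterion, and Section 11 makes the comparison only if possible. Read literally, the target is the proportion with an event during study observation, and the exact interval is valid for that. This stands, and it limits the weight of the point. It does not remove it: these are the primary estimates, the Synopsis announces the comparison without condition, and a rate with no horizon cannot be matched to any external rate.

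Four stronger readings are tempting, and the documents do not support them.

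- **That the exact interval is faulty.** Setting it against a 3-month risk tests a target the plan never set. An exact binomial would suit a fixed window with near-complete ascertainment.
- **That observation has no defined start.** Section 6 takes data from the procedure onward, and Section 10.3 captures events following it. What remains is that early infections in patients who never reached the first visit may be missing.
- **That Kaplan-Meier is the only acceptable estimator.** With L = 10% and k = 2 or 3, the event-or-completed binomial is closer to the truth.
- **That follow-up should be counted only from consent.** That would remove known early infections from a safety rate.

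It is also fair to say that the calculations concern infection only. Device-related events such as calcification, fibrosis or undesired remodeling may come later, so the fix must keep them visible.

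**Conclusion.** The point holds as a should-fix matter. It is certain from the text that neither primary endpoint has a horizon, that no analysis rule covers incomplete follow-up, and that the last visit is open-ended and depends on the site. It follows that the estimates average over unequal follow-up and are not aligned with any external rate.

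The size is not established. The ratios above rest on assumed risks, event timing, loss and a 12-month end that appears nowhere in the documents, and several scenarios show little or no effect. A reader might infer that the plan flatters the device. The documents do not support that: longer follow-up raises the crude rate, an all-enrolled denominator with loss lowers it, and missing early infections lower it. The net direction is unknown.

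**What to change.** In Section 11:

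1. Define both primary endpoints as occurring from the implant procedure through a fixed horizon that the schedule supports, for example the 3-month visit with a stated window.
2. Report the rate through that horizon with a 95% confidence interval and a stated rule for incomplete follow-up. Use either Kaplan-Meier with event-free subjects censored at last contact, or the exact binomial under both denominators (all enrolled; event or completed 3-month contact). Make the other the sensitivity analysis, and state that none of these corrects loss related to infection.
3. Keep events before consent in the rate. State beside it that it applies to patients who reached the first follow-up visit and consented, so early infections in others may be missing.
4. Report events after the horizon separately with person-time, including late device-related events.
5. Compare only with external rates for the same horizon, and make no comparison if none exists. Align the Synopsis with this.
6. Reconcile the first-visit wording in Section 1 and the single-visit wording in Section 10.2 with the multi-visit schedule in the Synopsis and Sections 6 and 9.

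The cost is Section 11 wording and routine analysis code. Onset dates are already requested. A last-contact date must be recorded if the separate case report form, not available here, lacks it. The downside is that later events leave the primary estimate and are reported apart.

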### **10.** Adverse Event Reporting

#### 10.1 Definitions

#### **Adverse Event (AE)**

Adverse event (AE) will be defined as any untoward medical occurrence, unintended disease or injury or any untoward clinical signs in subjects whether or not related to the device. This includes events related to the device and to the procedure involved. For this post market clinical study only events that relate to the use of the CanGaroo ECM will be collected and is defined below in Adverse Device Effect.

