#### Adverse Device Effect (ADE)

An Adverse Device Effect is defined as a clinical sign, symptom, or condition that is causally related to the device procedure, the presence of the device, or the performance of the device. Due to the temporal proximity of the AE to product administration, there is a reasonable possibility that the product may have caused the AE or may have contributed to the severity or duration of an event caused by other means.

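### The plan collects only CanGaroo-related adverse events but would compare other AEs with patients who had no CanGaroo, so the relatedness filter acts on the study side only

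*Combined protocol and SAP*

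**What the plan says.** Three parts of the combined protocol and SAP bear on this.

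- **Collection.** Section 10.1 first defines an adverse event broadly, including "any untoward clinical signs in subjects whether or not related to the device". It then narrows what the study gathers: "For this post market clinical study only events that relate to the use of the CanGaroo ECM will be collected", pointing to the Adverse Device Effect definition. The clinical data lists in the Synopsis and Section 9 match the narrow rule. Their only adverse event item is "CanGaroo ECM related adverse events", with infection information as a separate item.
- **Width of the filter.** An Adverse Device Effect is one "causally related to the device procedure, the presence of the device, or the performance of the device". The same definition adds that, given the timing, "there is a reasonable possibility that the product may have caused the AE" or contributed to it.
- **Analysis.** Section 11 plans a table: "The number and percentage of subjects with AEs and with device-related AEs will be presented by type of AE". It then plans an external comparison: "Similarly, if possible, the rate of other AEs will be compared by type to the rate without use of the CanGaroo ECM device". The external rates are to come from the HCUP databases and/or the literature. No relatedness restriction is stated for them, and no test or margin is given. The Synopsis announces an external comparison of outcomes without the conditional wording.

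**The concern.** The collection rule and the analysis plan do not fit together. A study event enters the count only if the investigator judges it related to the use of CanGaroo. An event in a patient without CanGaroo cannot be put to that judgement. If both sections are followed as written, the two rates count different things, and the difference in counting pulls the study rate down.

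If the comparison is made, part of an apparent advantage for some event type could come from the collection rule and not from the envelope. A reader could also take the AE column in the Section 11 table as all-cause, because Section 10.1 defines AEs that way, although the collection rule does not allow such a column. Neither output is a primary endpoint, so what is at stake is a misleading secondary result.

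**Working it through.** **Step 1. Set the rules side by side.**

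| Element | Study subjects | External patients |
|---|---|---|
| Event counted | Related to CanGaroo use (10.1) | No relatedness limit stated (11) |
| Can a CanGaroo-relatedness judgement be made? | Yes, by the investigator | No, there is no CanGaroo |
| Definitions, time windows, completeness | Protocol visits and CRF | Not stated |

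The first two rows differ by construction. The third leaves room for differences in either direction.

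**Step 2. Read the AE table under the collection rule.** If only related events are collected, the AE count in Section 11 equals the device-related count, or exceeds it only by such events as reach the database by another route. Examples are procedure-related events, which the Adverse Device Effect definition admits, infections recorded separately, or a submitted event later graded not related. None of these makes the count all-cause.

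**Step 3. Illustrate the size.** The plan gives no background rate, no benchmark and no share of events judged related, so there is no figure of its own to reproduce.

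- From the documents: n = 1000 (the ceiling in Section 6) and the exact 95% binomial interval. Section 11 specifies that interval for the two primary endpoints; it is borrowed here.
- Assumed: an external rate of 3%, treated as fixed and complete; the same true rate in study subjects (no device effect); and a share *f* of study events judged related and therefore collected.
- Yardstick, not in the plan: the whole interval lies below the external rate.

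The upper exact limit for 19 events in 1000 is 2.95%, and for 20 events it is 3.07%. The interval therefore lies wholly below 3% when 19 or fewer events are collected. The chance of that is P(X ≤ 19), with X binomial(1000, 0.03 × *f*):

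| *f* | Expected collected rate | Chance interval lies wholly below 3% |
|---|---|---|
| 1.00 | 3.00% | 2.0% |
| 0.95 | 2.85% | 3.8% |
| 0.90 | 2.70% | 6.6% |
| 0.80 | 2.40% | 17.7% |

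**Step 4. Let the external side be imperfect too.** If the external source captures only a share *c* of true events, the expected ratio of study rate to external rate is *f*/*c*. With *c* = 0.8 the external rate is 0.8 × 3% = 2.4%. The interval lies wholly below 2.4% at 14 or fewer events and wholly above it at 35 or more.

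- *f* = 0.8, *c* = 0.8: ratio 1; 1.9% wholly below and 1.9% wholly above. The two losses cancel.
- *f* = 1, *c* = 0.8: ratio 1.25; 19.9% wholly above. The error runs against the device.

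The filter itself pushes one way; the net error of the comparison need not.

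**The case against.** The strongest reply is that the filter may remove very little. The Adverse Device Effect definition covers the device procedure as well as the envelope and accepts a reasonable possibility of contribution. Section 10.3 lists bleeding, hematoma and seroma among device-related events. A pocket hematoma after implantation would usually qualify, so *f* may be close to 1 for these types, and the table above then shows almost no effect. This stands, and it is why no size can be claimed. It does not remove the mismatch: a causality judgement is still made on one side only.

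Second, every numerical input except n and the interval method is assumed, and no decision rule of this kind is planned. That also stands; the figures show sensitivity and predict nothing about this study.

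Third, the comparison is conditional and descriptive, and the CRF (a separate document), site training (Appendix D) or the sponsor's review of adverse events with sites (Section 12.1) may settle what is captured. That limits the weight of the point. The protocol's own two sections would still disagree.

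Three stronger readings are tempting and not supported.

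- A reader might infer that the comparison will favour the device overall. The external definitions, windows and completeness are unspecified, and Step 4 shows that they can cancel or reverse the effect.
- A reader might infer that Sections 10.2 and 10.3 contradict Section 10.1. The instruction "All serious and device related events must be reported immediately to Aziyo" may mean events that are both serious and related. The not-related grade may apply to an event already submitted, and the capture sentence in 10.3 may only name sources. These passages are ambiguous and do not amount to a contradiction.
- A reader might infer that the primary results are biased. The first primary endpoint is itself defined by relatedness, and infection information is a separate data item with no relatedness condition stated.

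**Conclusion.** The point holds in a limited form. Following Sections 10.1 and 11 together gives a one-sided comparison of other AEs and an AE count that cannot be all-cause. This rests on the text alone. All else equal, the filter lowers the study rate. By how much cannot be derived from the documents. Under the stated assumptions, the chance of an interval wholly below the external rate rises from 2.0% to 6.6% at *f* = 0.9 and to 17.7% at *f* = 0.8, and the effect is negligible near *f* = 1. The net direction against an unspecified external source is not established.

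The outputs concerned are secondary and descriptive, and the primary estimates are not shown to be affected. The plan should still be corrected, because the wording fix is cheap and events not collected may be impossible to recover at analysis.

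**What to change.** Reconcile Sections 10.1 and 11, and clarify Sections 10.2 and 10.3 so that one collection rule applies throughout.

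**Default, wording only.** Keep related-only collection. Label the AE counts in Section 11 as events collected under the Adverse Device Effect definition. Either drop the external comparison of other AEs, or report the rates descriptively with the one-sided filter stated beside them.

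**Alternative, if a real comparison is wanted.** Collect all events of the types to be compared regardless of attribution, and record relatedness as a separate item. Use the all-attribution counts with definitions and time windows matched to the external source. Restrict that analysis to subjects enrolled under the amended rule.

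**Cost.** Either route needs a protocol amendment with EC/IRB approval (Section 12.2), at up to 50 centers (Section 6). The default gives up the external comparison of other AEs as a comparison. The alternative adds a CRF change, more adverse event entries and a higher reported AE rate, and subjects enrolled earlier would not contribute to the comparison.
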